5.7. Study Drug Materials and Management

TAS-120 will be supplied by the Sponsor; fulvestrant will be supplied by the Sponsor or procured by investigative sites. Detailed information, including requirements for accountability, and disposal of study drug will be provided in a separate Pharmacy Manual.

5.7.1. Description of Study Drug

5.7.1.1. TAS-120

A description of the TAS-120 study drug and packaging information are provided in Table 8.

Table 8: TAS-120 Product Description and Packaging Information

Product Description and Dosage Form	Potency/ Strength	Appearance	Primary Packaging
TAS-120 Tablet	4 mg	Round, white, film-coated tablet	Aluminum/Aclar blister

5.7.1.2. Fulvestrant

Please refer to the PI for the description of fulvestrant.

5.7.2. Packaging and Labeling

TAS-120 tablets will be packaged in child-resistant Dosepak® cards. Labeling will identify tablet counts in each card. The Dosepak® cards will be labeled with at least the following:

- a. Protocol number
- b. Sponsor name
- c. Storage conditions
- d. Study drug name
- e. Tablet strength
- f. Lot number
- g. Number of tablets in each container
- h. Investigational caution statement

Additional clinical labeling will be added as required by local regulations.

Fulvestrant will follow the packaging and labeling specified on the PI and will receive additional clinical labeling as required by local regulations.

5.7.3. Study Drug Storage

TAS-120 tablets should be stored at room temperature (according to the country's regulatory definition for room temperature) in accordance with the label.

Fulvestrant should be stored per the storage conditions specified on the PI. All study medication must be kept in a locked area with access restricted to specific study personnel.

5.7.4. Drug Accountability

The Investigator is responsible for ensuring that all TAS-120 received at the site is inventoried and accounted for throughout the study. TAS-120 will be stored and disposed of according to the Sponsor's instructions. The dispensing of TAS-120 to the patient and the return of TAS-120 from the patient must be documented in the patient's source documents/the drug accountability form. Patients must be instructed to return all original containers, whether empty or containing study drug. Dose reductions, interruptions, and reason for these actions must be recorded in the patient's source documents and eCRF.

The Investigator is responsible for ensuring that all fulvestrant received at the site is inventoried and accounted for throughout the study.

At the conclusion of the study, all study drugs supplied by the Sponsor must be destroyed or returned to the designated depot, per the instructions provided in the Pharmacy Manual.

TAS-120 is not to be used outside of this study.

6. STUDY ASSESSMENTS

6.1. Study Assessments and Procedures

The Schedule of Events (Table 1) summarizes the frequency and timing of all applicable study assessments, including allowable windows for study visits and assessments / procedures. Written informed consent must be provided before any study-related procedures are performed.

6.1.1. Determination of FGFR1 or FGFR2 Amplification Status

Determination of eligibility is based in part on the determination of *FGFR1* or *FGFR2* amplification status per the following methods:

6.1.1.1. High-Level FGFR1 Amplification

- The patient must have an FGFR1/CEN8 ratio of ≥5 or an FGFR1 copy number ≥10 signals per cell determined in tumor tissue using next-generation sequencing (NGS), fluorescence in situ hybridization (FISH), or other assays that can determine gene amplifications in tumor tissues.
- May be based on local Clinical Laboratory Improvement Amendments (CLIA) or other similarly certified laboratory testing on tumor tissue using NGS, FISH, or another assay that can determine gene amplifications in tumor tissues.
- Archival or (preferably) fresh tumor tissue must be available for central laboratory confirmation of *FGFR1* amplification.

6.1.1.2. FGFR2 amplification

- May be based on local CLIA or other similarly-certified laboratory testing using NGS, FISH, or other assays that can determine gene amplifications in tumor tissues or circulating tumor DNA (ctDNA).
- Archival or (preferably) fresh tumor tissue must be available for central laboratory confirmation of *FGFR2* amplification.

6.1.2. General Assessments

The following general assessments are performed as indicated in the Schedule of Events.

- Demographics / medical history: Includes sex, age, race, clinical diagnosis, date and method of diagnosis, prior cancer therapy, and relevant medical history (past and concurrent).
- **Review eligibility criteria:** Eligibility is assessed during the screening period and should be confirmed on Day 1 of Cycle 1, prior to first dose of study therapy.
- Physical examination

- **Vital signs:** Pulse rate, systolic and diastolic blood pressure, body temperature, and respiration rate. Any abnormal reading should be repeatedly immediately.
- **Height and body weight:** Height is collected for the purpose of body mass index calculations at baseline only.
- ECOG performance status: See Appendix A.
- **Pregnancy test:** Serum β-human chorionic gonadotrophin (human chorionic stimulating hormone) test required for WOCBP at screening and end of treatment; serum or urine test required at all other timepoints listed in the Schedule of Events.
- Concomitant medication: Including all medications / therapies administered from the time ICF is signed through 30 days after administration of the last dose of study therapy or until the start of new anticancer therapy.
- **12-Lead electrocardiogram (ECG)**: Single, resting, semirecumbent 12-lead ECG will be performed locally. Data collection includes RR interval (heart rate), QT interval, QTcF interval and abnormal findings; the Investigator is responsible for interpreting and measuring ECG data.

6.1.3. Ophthalmological Examination

The cornea and conjunctiva are readily visible tissues, and therefore, abnormalities of the cornea and conjunctiva can usually be recognized via external ocular examination and routine slit lamp biomicroscopy. The retina is visible through fundoscopy after dilation of the pupil. Ophthalmologic examination will be performed at screening and 4-6 weeks after first dose; additional on-study evaluation as needed due to local requirements, physician judgment, and/or symptoms or signs of mineral deposits.

Each evaluation will encompass:

- 1 External ocular examination
- 2. Routine slit lamp biomicroscopy of anterior ocular structures, including the anterior and posterior chambers (Fluorescein or rose Bengal or other dyes used to evaluate the ocular surface can be used according to institutional guidelines and local clinical practice)
- 3. Dilation of the pupil with direct/indirect fundoscopy per institutional guidelines and local clinical practice

6.1.4. Laboratory Assessments

All laboratory assessments will be performed locally. The laboratory must provide normal reference ranges for hematology, chemistry and coagulation tests. Laboratory results for hematology, chemistry, and coagulation assessments must be reviewed for clinically significant events. Any clinically significant events must be followed and reported as required by the protocol (see Section 8.4.1).

• **Hematology assessments include:** Red blood cell count, hemoglobin, hematocrit, platelets, white blood cell count with differential (ANC, lymphocytes, monocytes, eosinophils, basophils)

- Coagulation assessments include: Prothrombin time-international normalized ratio, activated partial thromboplastin time, fibrinogen
- Chemistry (serum or plasma) assessments include: AST, ALT, alkaline phosphatase (ALP), total bilirubin, direct bilirubin, albumin, lactate dehydrogenase, inorganic phosphorus, triglyceride, total cholesterol, creatinine, urea or blood urea nitrogen, sodium, potassium, chloride, calcium, magnesium, blood glucose, creatinine clearance (if there is a measured value, use the measured value) or estimated glomerular filtration rate.

For a calculated creatinine clearance (Ccr) value, use the Cockcroft-Gault formula:

Male Ccr (mL/min) = Body wt (kg)×(140-age)[72×serum creatinine (mg/dL)] Female Ccr (mL/min) = male Ccr×0.85

6.1.5. Tumor Assessments/Scans

On-site tumor assessments (including computed tomography [CT]/magnetic resonance imaging [MRI]) will be performed by the Investigator/local radiologist according to RECIST 1.1 guidelines (Eisenhauer et al. 2009). Results of these assessments, including response for target and non-target lesions and appearance of new lesions, will be the basis for the continuation or discontinuation of study therapy. Response definitions are provided in Section 7.2.1.

If the Investigator determines that a patient has developed clinical disease progression manifested by symptomatic deterioration but not supported by radiologic evidence of progression, the patient may stop treatment. Symptoms of clinical disease progression must be documented in the patient's source documents and must be reported as AEs. Every effort should be made to document objective disease progression even after discontinuation of treatment.

The same method of assessment and the same technique must be used to characterize each identified and reported lesion at screening, throughout the study, and during the follow-up period. Please see Section 7 for more detailed discussion of efficacy evaluations.

Note that patients who discontinue without documented disease progression should continue to undergo tumor assessments/scans according to the Schedule of Events until PD is documented, new anticancer therapy is initiated, the study is terminated, or consent is withdrawn.

6.1.6. Safety Evaluations

For a detailed description of safety data collection, please refer to Section 8.

6.1.7. Pharmacodynamic Evaluations

For discussion of pharmacodynamic evaluations planned in this study, including collection of blood samples for ctDNA assessment and optional fresh tumor biopsies, please refer to Section 9.

6.1.8. Pharmacokinetic Evaluations

For discussion of PK evaluations planned in this study, including collection of blood samples, please refer to Section 9.

6.1.9. Survival Follow-Up

Please refer to Section 3.2.6.

7. EFFICACY EVALUATIONS

7.1. Efficacy Criteria

The determination of antitumor efficacy will be based on the results of objective tumor assessments/scans interpreted by the Investigator, according to RECIST 1.1.

7.1.1. Method of Imaging

All patients with and without measurable disease will be eligible for assessment. The same method of assessment and the same technique should be used to characterize each identified and reported lesion at each assessment timepoint. Imaging-based evaluation is preferred to evaluation by clinical examination when both methods have been used to assess the antitumor effect of treatment. All measurements should be recorded in metric notation using a ruler or calipers.

Contrast-enhanced CT scans or MRIs are the preferred methods for tumor assessments. If a contrast agent is contraindicated in a patient, obtain a non-contrast chest CT and enhanced MRI of the abdomen (and pelvis if clinically indicated). A spiral CT should be performed using a ≤5 mm contiguous reconstruction algorithm. Images must be acquired of the chest and abdomen (and pelvis if clinically indicated or obtained at Baseline) at each time point. Only CT scans and MRI may be used for tumor measurement.

Clinical lesions will only be considered measurable when they are superficial (eg, skin nodules, palpable lymph nodes). In the case of skin lesions, documentation by color photography, including a ruler to estimate the size of the lesion, is recommended.

Ultrasound should not be used to measure tumor lesions that are clinically not easily accessible for overall response evaluation (eg, visceral lesions). Ultrasound is a possible alternative to clinical measurements of superficial palpable nodes, subcutaneous lesions, and thyroid nodules. Ultrasound might also be useful to confirm the complete disappearance of superficial lesions usually assessed by clinical examination.

For additional guidance, refer to RECIST 1.1 specifications for standard anatomical radiological imaging.

7.1.2. Tumor Definitions

Measurable Lesions: Only measurable lesions can be selected as target lesions.

- Measurable visceral lesions: Lesions that can be accurately measured in at least 1 dimension with the longest diameter (to be recorded) ≥10 mm by CT scan if using slice thickness of ≤5 mm, or at least double the slice thickness of the CT or MRI scan if the slice thickness is >5 mm.
- Measurable pathological lymph nodes: A malignant lymph node must be considered
 pathologically enlarged with high suspicion of metastasis and measure ≥15 mm in the short
 axis when assessed by CT scan. The short axis is defined as the longest linear dimension
 perpendicular to the node's longest diameter as assessed within the same plane that the
 scan was acquired.

Non-measurable Lesions: All non-measurable lesions can only be selected as non-target lesions.

- Small visceral metastatic lesions that have a longest dimension <10 mm, or if slice thickness is >5 mm, less than twice the slice thickness
- Abnormal and suspected metastatic lymph nodes that are ≥10 mm to <15 mm in the short axis
- Truly non-measurable lesions (eg, ascites and peritoneal carcinomatosis)

Target Lesions:

- All measurable lesions up to a maximum of 2 lesions/organ and 5 lesions in total, representative of all involved organs/tissues should be identified as target lesions
- Target lesions should be selected on the basis of their size (visceral lesion with the longest diameter and lymph node with the measurement of short axis), be representative of all involved organs/tissues, but in addition should be those that lend themselves to reproducible repeated measurements
- When recording tumor measurements, the longest diameter will be measured for each non-nodal target lesion. For measurable pathological lymph nodes that may be identified as target lesions, the short axis measurement will be combined with the measurements of non-nodal (ie, visceral lesion) target lesions. Therefore, in cases of CR when abnormal nodes have been used as target lesions, the sum of diameters will not reduce to a null value.
- Target lesions will be followed up and measured at each subsequent timepoint.
- The sum of the diameters for all target lesions will be calculated and recorded. The baseline sum will be used as a reference to further characterize any objective tumor assessment in the measurable dimension of the disease.
- Assign a measurement to all target lesions regardless of size. An option of "too small to measure" will be provided if a measurement cannot be assigned. A value of zero should only be assigned in the case of a CR.
- An option of "not assessable" for a lesion will only apply to lesions that cannot be read due to technical reasons including:
 - CT artifact
 - Patient positioning where the lesions are obstructed or cannot be seen
 - Lesions that may not be seen in their entirety due to CT slice thickness
- In cases where a lesion divides into 2 lesions, the longest diameters of the fragmented portions should be added together to calculate the target lesion sum.
- In cases where 2 lesions coalesce, a plane between them may be maintained that would aid in obtaining maximal diameter measurements of each individual lesion. If the lesions have truly coalesced such that they are no longer separable, the vector of the longest diameter in this instance should be the maximal longest diameter for the "coalesced lesion."

Non-target Lesions:

- Non-target lesions include all non-measurable lesions and measurable lesions that have not been selected as target lesions.
- The primary lesion should always be classified as a non-target lesion irrespective of its size and whether or not it can be accurately measured.
- Lymph nodes that have a short axis <1 mm are considered non-pathological and should not be recorded.
- Any equivocal lesion without clear diagnosis (eg, uncharacteristic solitary lung nodule without biopsy, uncharacteristic thyroid mass lesion without fine needle aspiration) may be considered a non-target lesion if it cannot be differentiated from a benign lesion.
- All other lesions (or sites of disease), including pathological lymph nodes, should be
 identified as non-target lesions and should also be recorded at Baseline. Measurements are
 not required, but their presence, absence, or unequivocal progression should be followed
 throughout the study.
- It is possible to record multiple non-target lesions involving the same organ as a single item on the eCRF (eg, multiple enlarged pelvic lymph nodes or multiple liver metastases).

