4.1. Inclusion Criteria

A patient must meet all of the following inclusion criteria to be eligible for this study.

- 1. Patient provides written informed consent.
- 2. Patient is ≥18 years of age (or meets the country's regulatory definition for legal adult age, whichever is greater)
- 3. Eastern Cooperative Oncology Group (ECOG) performance status 0 or 1.
- 4. Histologically or cytologically confirmed recurrent locally advanced or metastatic breast cancer not amenable to treatment with curative intent, meeting all of the criteria for 1 of the following cohorts:

A. Cohort 1

- i. HR+ HER2- breast cancer harboring an *FGFR2* gene amplification. HR+ HER2- breast cancer is defined per the local pathology report as estrogen receptor (ER) >1% and/or progesterone receptor (PR) >1%, HER2-negative per American Society of Clinical Oncology (ASCO) and the College of American Pathologists (CAP) guidelines, 2018.
- ii. Measurable disease per Response Evaluation Criteria in Solid Tumors (RECIST) Version 1.1
- iii. Has received 1-3 prior endocrine-containing therapies and up to 2 prior chemotherapy regimens for advanced/metastatic disease
- iv. Has received prior treatment with a CDK4/6 inhibitor or is ineligible for such treatment (per Investigator decision)
- v. Has experienced disease progression/recurrence within 1 month following the completion of any endocrine therapy for advanced/metastatic breast cancer

B. Cohort 2

- i. TNBC harboring an *FGFR2* gene amplification. TNBC is defined as negative for ER, PR and HER2. Negative for ER and PR includes the following: local pathology report classifies them as negative, Allred Score of 2 or below or <1% staining. HER2-negative per ASCO / CAP guidelines, 2018.
- ii. Measurable disease per RECIST 1.1
- iii. Has received at least 1 prior chemotherapy or chemotherapy/immunotherapy (PD-L1/PD-1 inhibitors) regimen for advanced/metastatic disease
- iv. Has experienced disease progression/recurrence during or after the most recent prior chemotherapy for advanced/metastatic breast cancer

C. Cohort 3

- i. TNBC or HR+ HER2- breast cancer (defined as above) harboring an *FGFR2* gene amplification
- ii. Non-measurable, evaluable disease per RECIST 1.1. Patients with bone-only disease must have lytic or mixed lytic-blastic lesions
- iii. Other criteria for either HR+ HER2- breast cancer or TNBC should be met as described for Cohort 1 and 2, respectively

D. Cohort 4

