7.2.1.2. Objective Response Assessment

Assessments will be based on the definitions provided in Table 11 and Table 12.

Since this is a non-randomized study, all responses (CR/PR) must be confirmed.

Table 11: Time Point Response for Patients with Target (±Non-target) Disease

Target	Non-Target	New	Objective
Lesions	Lesions	Lesions	Response
CR	CR	No	CR
CR	Non-CR/Non-PD or Not all evaluated	No	PR
PR	Non-PD or Not all evaluated	No	PR
SD	Non-PD or Not all evaluated	No	SD
Not all evaluated	Non-PD	No	NE
PD	Any	Yes or No	PD
Any	PD	Yes or No	PD
Any	Any	Yes	PD

Abbreviations: CR=complete response; NE=not evaluable; PD=progressive disease; PR=partial response; SD=stable disease

Table 12: Time Point Response for Patients with Only Non-target Disease

Non-Target Lesions	New Lesions	Objective Response
CR	No	CR
Non-CR/Non-PD	No	SD
Not all evaluated	No	NE
Unequivocal PD	Yes or No	PD
Any	Yes	PD

Abbreviations: CR=complete response; NE=not evaluable; PD=progressive disease; PR=partial response; SD=stable disease

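### A patient in Cohort 1, 2 or 4 whose only measurable lesion is the breast primary is eligible and counted for ORR but cannot be scored PR

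*Protocol*

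**What the plan says.** **Eligibility (protocol 4.1, criterion 4).** Cohort 1 asks for "Measurable disease per Response Evaluation Criteria in Solid Tumors (RECIST) Version 1.1"; Cohorts 2 and 4 ask for "Measurable disease per RECIST 1.1". No cohort asks for a target lesion, or for a measurable lesion outside the breast.

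**Lesion classification (protocol 7.1.2).** The target-lesion rule covers "All measurable lesions up to a maximum of 2 lesions/organ and 5 lesions in total". The definition of a measurable lesion does not exclude the primary. The non-target rules then say "Non-target lesions include all non-measurable lesions and measurable lesions that have not been selected as target lesions", followed by "The primary lesion should always be classified as a non-target lesion irrespective of its size and whether or not it can be accurately measured".

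**Scoring.** Protocol Table 10 defines PR for target lesions as a 30% fall in the sum of their diameters. Protocol Table 12, headed "Time Point Response for Patients with Only Non-target Disease", allows CR, SD, NE or PD. SAP 6.4.1 derives overall response for patients with measurable disease from SAP Table 4, which starts from a target-lesion status. It describes derivation from non-target lesions alone for Cohort 3 only.

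**Denominator.** The Response Evaluable Set (protocol 10.3, SAP 5.3) requires measurable disease in Cohorts 1, 2 and 4. The SAP's main efficacy population (SAP 6.4) is treated patients with central confirmation of the amplification, and for Cohort 4 treatment at the recommended dose. Neither requires a target lesion.

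**The concern.** The classification rule foresees a primary that can be accurately measured and makes it non-target all the same, while the entry criterion looks only at measurability. A patient whose sole measurable lesion is the primary passes the second rule and, under the first, has nothing from which PR can be calculated.

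ORR is the primary endpoint in Cohorts 1 and 2 and drives both the Stage 1 futility decision and the final test. Patients who sit in the denominator but can respond only by complete disappearance pull ORR down. The risk is of missing a real effect, not of a false positive. In Cohort 4 the loss touches secondary ORR and, through it, which patients enter the DOR analysis.

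**Working it through.** **1. Trace one patient.** Take a Cohort 1 patient whose only measurable lesion is the breast primary.

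- Criterion 4: measurable disease is present, so the patient is eligible.
- Section 7.1.2: the primary is non-target, so there is no target lesion.
- Table 10: PR needs a sum of target diameters, and there is none. Table 10 also prints a PR label for non-target lesions, but it describes persisting disease; Table 12 turns non-CR/non-PD into SD, so the label does not help.
- Protocol Table 12: the result is CR, SD, NE or PD. A 60% shrinkage is recorded as SD.
- Protocol Table 11 and SAP Table 4: every route to PR needs target CR or target PR.
- SAP Table 4 has no row written for a patient without target lesions. The rows that accept any target status lead only to PD, so a patient without progression has no defined result under the SAP.
- The patient remains in the ORR denominator under both the protocol's and the SAP's efficacy population.

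**2. Reproduce the design (protocol 10.1).** Inputs for Cohorts 1 and 2: null 15%, target 30%, 19 patients in Stage 1, continue with at least 4 responders, 55 in total. With final cut-off c, the probability of rejecting at true rate p is

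P(p) = Σ (x = 4 to 19) C(19, x) pˣ (1 − p)¹⁹⁻ˣ × Pr[Bin(36, p) ≥ c − x].

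- A search for the optimal Simon design returns 19 then 55 patients, with rejection at c = 13. Exact alpha is 0.0477 and power 0.8006, which matches the stated 5% and 80%. The documents do not print 13.
- SAP 6.4.1 prints c = 15. That gives alpha 0.0119 and power 0.672. This mismatch is a separate issue, so both cut-offs are shown below.

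**3. Effect on power (illustration).** Let f be the share of patients whose only measurable lesion is the primary. The documents give no value, so f is an assumption. Suppose these patients truly respond at 30% and none reaches CR. The scorable rate is then 0.30 × (1 − f); for f = 5%, 0.30 × 0.95 = 28.5%.

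| f | Expected such patients of 19 / of 55 | Scorable ORR | Pass Stage 1 (at least 4 of 19) | Power, 13 or more of 55 | Power, 15 or more of 55 |
|---|---|---|---|---|---|
| 0% | 0 / 0 | 30.0% | 87% | 80% | 67% |
| 2% | 0.4 / 1.1 | 29.4% | 85% | 78% | 64% |
| 5% | 1.0 / 2.8 | 28.5% | 83% | 74% | 59% |
| 10% | 1.9 / 5.5 | 27.0% | 80% | 67% | 49% |

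**The case against.** **The rule on the primary may be a deliberate exception.** A reader might infer that section 7.1.2 flatly contradicts itself. It need not: the sentence on the primary can be read as a specific exception to the general target-lesion rule, and the sentence before it accepts that measurable lesions can be non-target. On that reading sites have no discretion, and inconsistent site practice is not shown. This stands. It does not close the gap between the exception and criterion 4.

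**PFS.** A reader might also infer that progression of a non-target primary is called later, so that PFS and 6-month PFS are inflated. The documents do not support that. Section 7.2.1.1.1 offers a test for unequivocal non-target progression set at a 73% increase in volume, equated with a 20% increase in diameter (1.2³ = 1.728). The call remains more subjective than a measurement, but no direction of bias follows.

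**Size.** Nothing in the documents says how often the primary is the only measurable lesion. In patients with recurrent or metastatic disease already treated for it, this may be uncommon. A patient with a primary and another measurable lesion selected as target is scored by Table 11 and can reach PR. CR remains possible even for a primary-only patient, so setting CR to zero overstates the loss. CBR in Cohorts 1, 2 and 4 can still count SD of at least 24 weeks where the protocol tables are applied. All of this stands and limits the point to a gap of unknown, possibly small, size.

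**Conclusion.** The point holds for one type of patient. Under the rules as written, a Cohort 1, 2 or 4 patient whose only measurable lesion is the breast primary is eligible, counts for ORR, and cannot be scored PR. The SAP also lacks a rule for scoring this patient when there is no progression. ORR is biased down; this matters most in Cohorts 1 and 2, where it is the primary endpoint. In Cohort 4 it affects secondary results only, and no bias in 6-month PFS has been shown.

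The existence of the gap rests on the text alone. Its size rests on an assumed share and on no CR in these patients. At a share of 2% the cost is 2 to 3 points of power (80% to 78%, or 67% to 64%). At 10% it is 13 to 18 points (80% to 67%, or 67% to 49%), depending on the cut-off. RECIST itself was not consulted; the reading of measurable disease is the protocol's own.

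**What to change.** 1. In protocol 7.1.2, replace the sentence on the primary with: *A primary lesion that meets the measurability criteria may be selected as a target lesion under the same rules as any other lesion.* This agrees with the general target-lesion rule and with criterion 4. Alternatively, keep the sentence and require at least one measurable lesion other than the primary in Cohorts 1, 2 and 4.
2. In SAP 6.4.1, state how any Cohort 1, 2 or 4 patient without a target lesion is scored. This is needed under either option, because such patients may already be enrolled.

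The cost is a sentence in a protocol amendment, a rule in the SAP, and matching text in the imaging and eCRF guidelines. No scans are added. The small downside is that baseline target selection must be checked for enrolled patients with a measurable primary.

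A separate, minor point: section 7.1.1 says "Only CT scans and MRI may be used for tumor measurement", yet the same section treats superficial clinical lesions as measurable and lets ultrasound stand in for clinical measurement of some of them. The sentence should be reconciled with both allowances.
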